## Objectives, Estimands, and Endpoints

Objectives	Estimands	Endpoints
Primary:	Primary:	Primary:

To characterize the safety profile of tafamidis once daily for the treatment of Chinese ATTR-CM patients in clinical practice.

	

Not applicable.

	

Incidence of treatment-emergent adverse events.

Secondary:		Secondary:

To characterize the descriptive efficacy of tafamidis once daily in Chinese ATTR-CM patients

To characterize tafamidis PD in Chinese ATTR-CM patients.

To characterize the impact on quality of life of tafamidis once daily for the treatment of Chinese ATTR-CM patients.

To characterize tafamidis PK in Chinese ATTR-CM patients.

	

Not applicable.

	

Assessment of 6-MWT, NT-pro BNP at scheduled visits.

TTR stabilization and TTR concentration at Baseline (pre dosing) on Day 1, at Months 1, 6, and 12 (or End of Treatment (EOT)).

Kansas City Cardiomyopathy Questionnaire overall summary scores, EQ-5D-5L index scores and EQ-5D VAS scores, 12-Item Short Form Survey (SF-12) scores, at Day 1, Months 6, 12 (or End of Treatment (EOT)).

PK: plasma concentrations of tafamidis at Months 1, 6, and 12 (or EOT).

## Overall Design

This is a national, multi-center, single-arm study, open-label to patients with symptomatic ATTR-CM who are tafamidis naïve. This study is to obtain safety, descriptive efficacy, PK and PD data for tafamidis 61 mg soft capsule orally once daily, with or without food.

Participants with New York Heart Association (NYHA) class greater than or equal to III should not make up more than 1/3 of all enrolled participants

Investigators will confirm the eligibility of each participant to meet inclusion/exclusion criteria. Participant eligibility for participation in the study will receive tafamidis 61 mg once daily or 12 months following the assessment as the screening and baseline, month 1, 3, 6, 9 and 12 visits (or End of Treatment visit).

Patients will continue to receive their current medications and all other standard care for their disease. The use of permitted concomitant medication must be in accordance with approved tafamidis package insert. Concomitant medication not permitted in this study is described in [Section 6.5](#).

Participants will complete protocol required tests and procedures as described in [schedule of activities](#). A final study report will be completed approximately 3 years after the date of the first tafamidis patient enrollment in the study.

Scheduled Visits: Day 1, Months 1, 3, 6, 9,12 (or End of Treatment) and a Post-treatment follow-up.

### **Number of Participants**

At least 53 participants need to be treated. Refer to [Section 9.2](#) for detailed information on sample size determination.

### **Intervention Groups and Duration**

Total duration of study participation for each participant receiving tafamidis once daily with approved dose is 12 months (or Early Study Discontinuation). Follow-up visit dates should be based on the date of the Baseline visit.

### **Data Monitoring Committee:**

The study will not use an data monitoring committee (DMC).

### **Statistical Methods**

In order to attain an 80% probability of observing at least 1 participant having an event for TEAEs with incidence rate of 3%, at least 53 participants need to be treated.

Descriptive analyses will be performed.

#### **1.2. Schema**

Not applicable.

### 1.3. Schedule of Activities (SoA)

The SoA table provides an overview of the protocol visits and procedures. Refer to the **STUDY ASSESSMENTS AND PROCEDURES** section of the protocol for detailed information on each procedure and assessment required for compliance with the protocol.

The investigator may schedule visits (unplanned visits) in addition to those listed in the SoA table, in order to conduct evaluations or assessments required to protect the well-being of the participant.

Procedure/ Assessment	Screening	Baseline visit	Month a					
			1 (±1 week)	3 (Tel eph one visit ±2 weeks)	6 (±2 week s)	9 (Tel eph one visit ±2 weeks)	12 (±2 weeks) (or within 2 weeks after End of Treatment)	Post- treatment follow-up (28+7 days after last dose)
	Day-45 to Day 0	Day 1						
Informed Consent	X							
Medical History	X							
Review entrance criteria	X	X						
Full physical examination	X							
Brief physical examination		X	X		X		X	
Height	X							
Weight	X	X	X		X		X	
12 Lead ECG	X	X	X		X		X	
Vital signs b	X	X	X		X		X	
Echocardiogram	X				X		X	
Tissue biopsy or radionuclide bone scintigraphy (99mTc-PYP) c	X							
Laboratory samples								
Hematology	X		X		X		X	
Serum Chemistry	X		X		X		X	
Coagulation (INR, PT, APTT, FIB)	X		X		X		X	
Thyroid-stimulating hormone, total Thyroxine 4 and free Thyroxine 4		X	X		X		X	
Retinol Binding Protein		X			X		X	
Contraception check d	X			X	X	X	X	X
Pregnancy test (only for WOCBP) e	X				X		X	
Serology (HBsAg, anti- HCV, anti-TP and anti-HIV)	X							
Serum/urine test for primary amyloidosis (AL)	X							

Procedure/ Assessment	Screening	Baseline visit	Month a					
			1 (±1 wee k)	3 (Tel eph one visit ±2 wee ks)	6 (±2 week s)	9 (Tel eph one visit ±2 wee ks)	12 (±2 weeks (or within 2 weeks after End of Treatment)	Post- treatment follow-up (28+7 days after last dose)
	Day-45 to Day 0	Day 1						
Mass spectrometry/ Immunohistochemistry f	X							
Genotyping g	X							
Urinalysis	X		X		X		X	
NT – proBNP, Troponin I		X			X		X	
6-MWT		X			X		X	
TTR stabilization, TTR concentration h		X	X		X		X	
Tafamidis concentrations i			X		X		X	
KCCQ j		X			X		X	
EQ-5D-5L k		X			X		X	
SF-12 k		X			X		X	
NYHA classification	X	X			X		X	
Concomitant treatments	X	X	X	X	X	X	X	
Serious and nonserious adverse event monitoring	X	X	X	X	X	X	X	X
Hospitalization determination		X	X	X	X	X	X	
Documentation of vital status		X	X	X	X	X	X	
Record time of dosing		X	X		X		X	
Record dosing adherence			X		X		X	
Dispense investigational drugs		X	X		X			

- Visits, if applicable, are typically defined with respect to the Baseline visit and in accordance with expectations on the standard of care and/or required procedures for the study.
- Systolic and diastolic blood pressure (semisupine at least 5 minutes prior to assessment), pulse rate, respiratory rate and body temperature
- Biopsy or radionuclide bone scintigraphy (99mTc-PYP) for amyloid documentation must be performed at Screening or have been performed and documented within 5 years of enrollment. If greater than 5 years, biopsy or radionuclide bone scintigraphy (99mTc-PYP) must be repeated at the investigative site.
- Refer to [Appendix 4](#) for Contraceptive Guidance and Collection of Pregnancy Information.
- For women of childbearing potential. Refer to [Appendix 4](#) for Woman of Childbearing Potential (WOCBP).
- For those absence of a variant TTR genotype, absence of radionuclide bone scintigraphy (99mTc-PYP) and presence of amyloid deposits in biopsy tissue.
- Repeat not required if there is documentation of genotyping result confirming the TTR gene mutation within 5 years of enrollment.
- TTR stabilization and TTR concentration: baseline (Day 1) sample: collect pre-dose during the clinic visit. Month 1 sample: collect pre-dose and at 3 hours (±1.5 hours) post-dose. Month 6 sample: collected at

Procedure/ Assessment	Screening	Baseline visit	Month a					
			1 (±1 wee k)	3 (Tel eph one visit ±2 wee ks)	6 (±2 week s)	9 (Tel eph one visit ±2 wee ks)	12 (±2 weeks) (or within 2 weeks after End of Treatment)	Post- treatment follow-up (28+7 days after last dose)
	Day-45 to Day 0	Day 1						

7 hours (±2.5 hours) post-dose. Month 12 sample: collect at 1 hour (±30 minutes) post-dose, or End of Treatment sample: collect at time during the clinic visit. Please refer to [Section 8.6](#) for details.

- i. Tafamidis concentrations: Month 1 tafamidis concentration sample: collect pre-dose and at 3 hours (±1.5 hours) post-dose; Month 6 tafamidis concentration sample: collect at 7 hours (±2.5 hours) post-dose; Month 12 sample: collect at 1 hour (±30 minutes) post-dose, or End of Treatment sample: collect at time during the clinic visit. Please refer to [Section 8.5](#) for details.
- j. Kansas City Cardiomyopathy Questionnaire (KCCQ) should be completed before the EQ-5D-5L.
- k. EuroQoL-5 Dimensions (EQ-5D-5L) and SF-12 to be completed after the KCCQ.

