### 8.2.8. Pregnancy Testing

Pregnancy tests should be serum tests, but must have a sensitivity of at least 25 mIU/mL. Pregnancy tests will be performed in WOCBP at the times listed in the [SoA](#). A negative pregnancy test result will be required prior the participant's receiving the tafamidis. Pregnancy tests will also be done whenever 1 menstrual cycle is missed during the active treatment period (or when potential pregnancy is otherwise suspected) and at the end of the study. Pregnancy tests may also be repeated if requested by institutional review boards (IRBs)/ethics committees (ECs) or if required by local regulations.

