### 10.4.2. Female Participant Reproductive Inclusion Criteria

A female participant is eligible to participate if she is not pregnant or breastfeeding, and at least 1 of the following conditions applies:

- Is not a WOCBP (see definitions below in [Section 10.4.3](#)).

OR

- Is a WOCBP and using a contraceptive method that is highly effective (with a failure rate of <1% per year), as described below, during the intervention period and for at least 28 days after the last dose of study intervention, which corresponds to the time needed to eliminate any reproductive safety risk of the study intervention. The investigator should evaluate the effectiveness of the contraceptive method in relationship to the first dose of study intervention.

The investigator is responsible for review of medical history, menstrual history, and recent sexual activity to decrease the risk for inclusion of a woman with an early undetected pregnancy.

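### The only scheduled pre-dose pregnancy test for women of childbearing potential is at Screening, with no limit on its age, so the test condition for first dose can be met by a result up to 45-46 days old

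*Protocol*

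**What the plan says.** Protocol section 1.3 (Schedule of Activities, SoA) has a row beginning "Pregnancy test (only for WOCBP". It carries a mark at Screening, Month 6 and Month 12 (or end of treatment); the Baseline/Day 1 cell is empty. The contraception-check row is marked at Screening but not on Day 1. The entrance-criteria row is marked at both.

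Section 8.2.8 takes the timing of tests from the SoA and adds: "A negative pregnancy test result will be required prior the participant's receiving the tafamidis". It gives no maximum age for that result. It calls for additional tests "whenever 1 menstrual cycle is missed during the active treatment period (or when potential pregnancy is otherwise suspected"), and it states: "Pregnancy tests may also be repeated if requested by institutional review boards (IRBs)/ethics committees (ECs) or if required by local regulations".

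Section 10.4.2 makes not being pregnant an eligibility condition. It requires that a woman of childbearing potential (WOCBP) is "using a contraceptive method that is highly effective (with a failure rate of <1% per year"), and it states the period as "during the intervention period and for at least 28 days after the last dose of study intervention". It also says: "The investigator should evaluate the effectiveness of the contraceptive method in relationship to the first dose of study intervention". It gives the investigator this further task: "review of medical history, menstrual history, and recent sexual activity to decrease the risk for inclusion of a woman with an early undetected pregnancy".

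Section 5.3.1 has the participant affirm correct contraceptive use at the SoA time points. It also has her told to contact the site at once if the method is stopped or pregnancy is known or suspected.

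Section 6.1.1 puts the first dose on Day 1, after the baseline procedures.

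**The concern.** The protocol itself makes a negative test a gate to treatment. A result more than six weeks old can satisfy that gate without showing whether the woman is pregnant on the day she is dosed. If she conceived after the Screening test and neither she nor the investigator suspects it, no scheduled procedure would detect the pregnancy before the first capsule. The next scheduled test is at Month 6.

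What is at stake is fetal exposure. The protocol takes this seriously: section 8.3.5.1 requires a report within 24 hours of awareness whether or not a serious adverse event has occurred, and refers exposures to a dedicated pregnancy-outcomes programme. The documents do not quantify fetal risk. The package insert is the safety reference (section 2.3) and is not among them, so the severity of the harm cannot be judged here.

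**Working it through.** **Inputs**

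- Screening window: Day -45 to Day 0 (protocol 1.3); Day -45 to Day -1 (SAP 2.3).
- First dose: Day 1 (protocol 6.1.1).
- Contraceptive failure rate: below 1% per year (protocol 10.4.2). I use 1% and assume the method is in use throughout screening.
- Number of WOCBP: not stated.

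**Age of the test at first dose.** The plan states no figure for this, so there is none to reproduce.

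- With a Day 0, as in the SoA: 1 - (-45) = 46 days.
- Without a Day 0, as in the SAP: 46 - 1 = 45 days.

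These are maxima. A test later in screening is correspondingly fresher.

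**Chance of conception between test and dose, per woman.** At a constant 1% per year over d days, the chance is 1 - 0.99^(d/365.25).

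| Interval (days) | Chance per woman |
|---|---|
| 46 | 0.126% |
| 45 | 0.124% |
| 23 (test midway) | 0.063% |

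These figures take no credit for cases caught by the history review or by suspicion.

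**Across several women.** The counts here are assumed for illustration only. The chance of at least one such pregnancy among k women over 46 days is 1 - (1 - 0.00126)^k:

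- k = 1: 0.13%
- k = 3: 0.4%
- k = 10: 1.3%

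**Likely number of WOCBP.** Mean age in the pivotal study was 74 (protocol 1.1), and section 10.4.3 counts women aged 60 or over as postmenopausal. Entry is open from age 18 (section 5.1). Few are likely, and there may be none.

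**Does any existing safeguard require a test before first dose?**

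| Safeguard | Requires a repeat test when nothing is suspected? |
|---|---|
| Day 1 entrance-criteria review (1.3, 10.4.2) | No; the scheduled test behind it is the Screening one |
| Menstrual and sexual history review (10.4.2) | No; a judgement |
| Contraceptive evaluation relative to first dose (10.4.2) | No; a judgement |
| Contraception check at Screening (1.3, 5.3.1) | No; lowers the risk only |
| Instruction to contact the site (5.3.1) | No; needs a stopped method or a known or suspected pregnancy |
| Missed-cycle trigger (8.2.8) | No; tied to active treatment |
| Suspicion trigger (8.2.8) | No; needs suspicion |
| Ethics-committee or local-rule repeats (8.2.8) | Only if asked for |

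**The case against.** The strongest reply is that a negative test is necessary for dosing but not sufficient. Eligibility requires that the woman is not pregnant, and entrance criteria are reviewed again on Day 1. Section 10.4.2 makes the investigator responsible for a history review aimed at early undetected pregnancy. A reader might infer from the SoA that an old negative result clears a woman for treatment by itself. The documents do not support that reading. The gap is narrower: the *test* condition can be met by an old result, and the remaining checks are not tests.

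A reader might also infer that conception risk during screening is uncontrolled, because the duration clause in 10.4.2 starts with the intervention period. That goes too far. A contraception check is scheduled at Screening, eligibility is worded in terms of a woman already using a method, and 5.3.1 has her told to report a stopped method or a suspected pregnancy at once. These partly support the 1% assumption. They do not prove it, since screening is not named in that clause.

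Nor do the SoA and 8.2.8 contradict each other. Screening precedes dosing, 8.2.8 defers to the SoA, and no rule in the documents is broken. Ethics committees or local rules may add tests, and the package insert may say more, but neither can be relied on from these documents.

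All of this stands and limits the point. It does not remove it, because nothing in the plan requires a repeat test before first dose when no one suspects pregnancy.

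**Conclusion.** The point holds as a minor gap in participant safety. The test condition for first dose can be met by a result up to 45 or 46 days old, and an unsuspected pregnancy conceived during screening could be dosed.

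The residual risk is very small: about 0.13% per woman at the longest interval and less with a later test. This rests on a method failing at 1% per year being in use throughout screening. If it is not, the risk is higher by an amount the documents do not allow one to state. The expected number of affected women is smaller still, because there may be few or no WOCBP.

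It would be wrong to read this as a threat to the trial's conclusions. The primary endpoint, the 53 participants and the analysis are untouched.

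**What to change.** - In the SoA, add a mark at Baseline/Day 1 for the WOCBP pregnancy test and for the contraception check.
- Run the test on the Day 1 blood draw, which is already taken for thyroid tests, NT-proBNP and transthyretin measurements.
- Amend 8.2.8 to require that negative Day 1 result before the first dose. Section 6.1.1 already places dosing after the baseline procedures.
- If serum results would take too long, amend 8.2.8 further to allow a urine test at the site on Day 1 with a sensitivity of at least 25 mIU/mL. This needs its own wording: 8.2.8 calls for serum tests, and the urine provision in 10.10.3.1 covers only home testing in public emergencies.
- Keep the history review and the suspicion trigger, because a Day 1 test can miss a very recent conception.

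The cost is two SoA marks, a short change to 8.2.8, one extra assay per WOCBP with no added venepuncture, and possibly a short wait before first dose. The maximum age of the last negative result falls from 45-46 days to the same visit.

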## 2. INTRODUCTION

### 2.1. Study Rationale

ATTR-CM is listed in 1st Chinese Rare Disease list released in 2018 under Idiopathic Cardiomyopathy category. Based on China regulatory regulation on encouragement for rare disease medication development, Pfizer plans to bridge the pivotal efficacy and safety data and Japanese pharmacokinetic (PK) data to apply for conditional approval with a post approval commitment study design.

Tafamidis is a small molecule that has been demonstrated to stabilize transthyretin. meglumine 20 mg soft capsule taken orally once daily has already been approved in the European Union for the treatment of Transthyretin Amyloid Polyneuropathy (ATTR-PN) in adult patients with stage 1 symptomatic polyneuropathy in 2011. In Japan, tafamidis meglumine 20 mg soft capsule once daily has also been approved by the Ministry of Health, Labor and Welfare (MHLW) to delay the peripheral neurological impairment of transthyretin familial amyloid polyneuropathy in September 2013, and tafamidis meglumine 4 x 20 mg once daily approved to delay the progression of Transthyretin Amyloid Cardiomyopathy (ATTR-CM) in March 2019. Tafamidis meglumine 4 x 20 mg once daily and tafamidis 61 mg have been approved in the United States in May 2019 for the treatment of the cardiomyopathy of wild type or hereditary transthyretin-mediated amyloidosis in adults to reduce cardiovascular mortality and cardiovascular-related hospitalization. Tafamidis has been approved in Europe in February 2020 for the treatment of ATTR-CM. In China, tafamidis meglumine capsule 20 mg once daily has already been approved for the treatment of ATTR-PN in adult patients with stage 1 symptomatic polyneuropathy in February 2020; 61 mg tafamidis soft capsule orally once daily was approved in September 2020 for the treatment of ATTR-CM.

The purpose of the study is to collect safety, descriptive efficacy, PK, and PD of tafamidis data in Chinese ATTR-CM patients, following the approval of tafamidis 61 mg for ATTR-CM indication in China.

### 2.2. Background

ATTR-CM occurs when transthyretin (TTR) amyloid fibrils infiltrate the myocardium, leading to deposits of extracellular amyloid. Deposition of transthyretin fibrils occurs between the myocardial cells and produces a thickening and stiffening of the myocardial tissue. This infiltration of the myocardium results in diastolic dysfunction progressing to restrictive cardiomyopathy, congestive heart failure, and ultimately death. There is a high unmet need to treat transthyretin amyloid cardiomyopathy, which is a life threatening, rare disease. Only 60 Chinese cardiac amyloidosis case reports were published from 2002-2017, and ATTR-CM is extremely rarely reported. One of 60 cases was diagnosed as ATTR-CM, 2 of them were just suspected one.

China Health Authority has released guidance on PAC study design of the post approval commitment study. A prospective observation study, single-arm cohort study is suggested to evaluate adverse events and other related safety risks. The study is to collect TEAEs that

were observed in previous ATTR-CM studies, defined as AEs with a small numeric higher incidence observed in the tafamidis treatment group compared with placebo; noted as AEs of clinical importance for treatment with tafamidis.

### 2.2.1. Clinical Overview

Tafamidis is an oral small molecule, under development by Pfizer, as a disease modifying therapy for TTR amyloid diseases. It binds to the thyroxine binding sites on the TTR tetramer, thereby preventing destabilization into the monomeric form which can deposit as amyloid fibrils in the extracellular space. It has been demonstrated to bind selectively to TTR (also referred to as pre-albumin) in human blood and slow fibril formation in vitro. It binds to the 2 thyroxine binding sites with negative cooperativity, exhibiting dissociation constants of 2 nM [ $K_{d1}$ ] and 154 nM [ $K_{d2}$ ] and kinetically stabilizing the TTR tetramer when bound (Sekijima 2009).

Study Fx1A-105 (B3461016) was a Phase 1 study of tafamidis meglumine PK in mild or moderate hepatic impairment participants and age, weight, and gender-matched healthy volunteers. The results indicated dosage adjustment is not necessary in participants with mild to moderate hepatic impairment. Study B3461009 was a Phase 1 Study to evaluate the safety, tolerability, PK and pharmacodynamics (PD) of PF-06291826 (tafamidis meglumine) after single oral administration of 20 mg and 40 mg tafamidis meglumine soft capsules to Japanese and Western healthy participants. Mean PK parameters and PD results (TTR percent stabilization) of Japanese participants were similar to those in Western participants thus suggesting no significant ethnic differences in PK and PD.

The potential for enzymatic and transporter mediated tafamidis drug-drug interaction (DDI) was evaluated at the projected clinical tafamidis doses of 20 mg/day tafamidis meglumine and 61 mg/day tafamidis free acid (called as tafamidis in the texts hereafter) doses in multiple nonclinical and one clinical drug-drug interaction (DDI) study (Fx1A-109 [B3461018]). Results from these studies have found that the potential of clinically significant PK drug-drug interactions with tafamidis is low.

Study Fx-002 (B3461015) was a Phase 1 study designed to evaluate the safety, tolerability, and pharmacokinetics of orally administered tafamidis in healthy male and female volunteers at single doses up to 120 mg and 3 multiple escalating doses (15, 30 and 60 mg) administered as solution in comparison to placebo once daily over 14 days. Study Fx1A-109 was a Phase 1 study in healthy volunteers designed to evaluate the cytochrome P450 induction potential of tafamidis 20 mg administered for 14 days. In Fx-002, the mean (standard deviation) maximum observed drug concentration ( $C_{max}$ ) value on Day 14 for the 60 mg solution was 4.40 (1.16)  $\mu$ g/mL. The mean (standard deviation)  $C_{max}$  on Day 14 for the 20 mg capsule was 2.66 (0.55)  $\mu$ g/mL in Fx1A-109.

There were no dose-limiting safety or tolerability issues noted during the Phase 1 program in healthy participants up to a single dose of 480 mg or multiple doses up to 60 mg. Further, a single oral dose of 20 mg tafamidis was well tolerated by participants with moderate or mild hepatic impairment. During Study B3461045, 2 patients experienced an acute overdose.

[figure not shown]
Both involved the accidental ingestion of a single tafamidis dose of 160 mg without the occurrence of any associated adverse events .

Study B3461040 was a Phase 1, randomized, double-blind, crossover, ascending dose escalation study to assess the safety and pharmacokinetics of tafamidis doses greater than 120 mg as oral solution in healthy participants. Single doses of tafamidis meglumine up to 480 mg were well tolerated in the study population of healthy adult Asian men.

The transthyretin (TTR) % stabilization data from Study B3461040 ([Figure 1](#)) suggest that a plateau is achieved as the molar ratio (MR) of tafamidis: TTR plasma concentration increases. Based upon the data available prior to conducting Study B3461040, it was believed that exposures achieved following a tafamidis dose of 20 mg once daily (QD) were sufficient to approach the TTR % stabilization plateau. The data from Study B3461040 suggest that doses higher than 20 mg provide a greater degree of stabilization, as measured by the [CCI](#) [REDACTED]. While the long-term risk-benefit of doses higher than 20 mg QD is unknown, it is reasonable to postulate that greater TTR stabilization has the potential to provide additional efficacy.

In order to calculate molar ratios at various tafamidis exposures, a TTR concentration must be assumed. Mean TTR concentrations observed at baseline in Study Fx-005 (B3461020) (24.7 mg/dL) and in patients with V122I mutations in Study Fx1B-201 (13.5 mg/dL) and the Transthyretin Amyloid Cardiac Study (TRACS) (14.9 mg/dL) are assumed for the calculations that follow: a 20 mg QD tafamidis dose at steady state produces a mean MR in the range of 1.2 to 3.2 from mean minimum drug concentration at steady state ( $C_{min,ss}$ ) to maximum drug concentration at steady state ( $C_{max,ss}$ ), which is below the plateau region of the data depicted in ([Figure 1](#)). Mean  $C_{min,ss}$  to  $C_{max,ss}$  following tafamidis doses of 80 mg are expected to produce MR values of 3.5 to 9.6, which are approaching or on the plateau region of TTR % stabilization.

